I prefer that my doctor make the final decision about which treatment will be used but seriously consider my opinion.	My doctor made the final decision about which treatment would be used but seriously considered my opinion.	I made the final decision about which treatment the patient would receive after seriously considering the patient's opinion.
I prefer to leave all decisions regarding my treatment to my doctor.	My doctor made all the decisions regarding my treatment.	I made the final decision about which treatment the patient would receive.

Recording of clinical consultations has been well-studied as a tool for determining patient-centered communication [1-3]. Therefore, all clinic encounters will be digitally recorded, transcribed, and analyzed using the OPTION scale for patient involvement, which is described below. The transcriptions will be de-identified and coded by independent raters (paid graduate students).

Assessments of QOL and decision regret will be performed at early (2 to 6 weeks) and later (6 months) timepoints after the clinic visit. These scales will be distributed electronically and patients will receive a phone call from the study coordinator to remind them to complete the measures. If they have not completed the measures by one week from the reminder phone call, a second call will be placed with an offer to complete the surveys over the phone with the study coordinator.

Chart review of all participants will be reviewed at the 6 month time point to assess for decisions ultimately made and completion or intention to complete recommended therapies. This timeframe was selected because the majority of patients will have completed their surgery, chemotherapy (if needed), and radiation (if needed) or at least have the initiation of these therapies planned. Radiation is always given last and this therapy is the most likely to still be in the planning stages. Also at this time point, endocrine therapy will have been initiated by some patients and may be planned by others.

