Intervention: The intervention will take place in the second half of the study, where the research assistant will inform the provider of the patient's preferred role based on the Patient Preference Scale prior to the clinic visit. The provider will then have a brief conversation at the beginning of the clinic visit where they state "I see that you prefer to have treatment decisions made (*together, by yourself, by me*) today. I appreciate knowing this information." The rest of the encounter will proceed as per the provider's usual practice. All other study procedures will be the same and the same perception scales will be used after the clinic visit and concordance and discordance will be examined as described in the study flow diagram.

Outcomes: The primary outcomes will be role concordance and patient satisfaction with the decision process. Secondary outcomes will be role perception concordance between provider and patient, quality of life at 2 to 6 weeks and 6 months after initial clinic visit, decision regret at 2 to 6 weeks and 6 months after initial clinic visit, and completion or planned completion of recommended therapies at 6 months. These time points were chosen to provide an early assessment of the impact of the intervention and to see if the results are durable after a longer period of time while still allowing us to conclude the study within the funding timeframe. There is evidence that decision regret is stable over time out to 4 years after diagnosis [4]. We will also correlate role

preference and concordance with surgical procedure performed or planned to look for associations between these measures and type of surgery received or planned, controlling for ineligibility for breast conservation.

Risks and Benefits of Participation: Participation is completely voluntary and may be withdrawn at any time. This is a low risk study, but some patients may experience distress from the questions on the surveys. If a patient experiences distress, she will be referred to our in-clinic Licensed Care Social Worker and she will make appropriate referrals to psychiatric care if necessary. There is also a low risk of loss of privacy and patients will be made aware of this. The benefits of participation are greater patient awareness of their own preferences and decisions.

Please see the study flow diagram on the following page.

Record decisions made and intentions
to complete therapy

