Data Management: All surveys will be administered electronically (tablets will be used for in clinic surveys) and stored on a secure University server. The surveys will be collected both in person (when the patient is in clinic) and electronically. The surveys will be built into and collected in the Research Subject Registry (RSR) database. Only study personnel will have access to the data and the PI will be responsible for deciding the role and level of access for each person. All digital audio recordings will be stored on a secure, password protected University computer in a locked office at Huntsman Cancer Institute. Again, only study personnel will have access to this data. The digital recordings will be transcribed and de-identified for coding and analysis. The de-identified transcripts will only be available to trained coders, the PI, and study coordinator. The electronic transcriptions will be stored on University based, password protected computers in the secured office area of the PI. Badge access is required to enter the office area during non-business hours. Paper versions will only be used if necessary due to computer outages or significant feasibility issues with the electronic transcripts and will be stored in a locked filing cabinet in the PIs locked office. Again, access will only be given to study personnel.

Statistical Analysis:

We are interested in evaluating whether patients play their desired role in treatment planning, and whether informing providers of patients' preferred roles improves patients' perception of achieving their desired role. Specifically, we will study two groups of patients, a non-intervention control group, where providers are blind to the patient's preferred decision making role and an intervention group where the provider is informed of the patient's preferred role. For this study we plan to enroll 100 patients, where the first 50 will be in the no intervention group and the next 50 will be in the intervention group. We expect the results to provide preliminary data for powering a larger extramural grant.

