f) OPTION assessment of patient involvement. The outcome of patient involvement at the clinic encounter will be measured using the OPTION scale. This scale was developed to measure the extent to which providers involve patients in decisions. A description of the measures used and timeline is illustrated in Table 2. With this scale, 2 independent raters will use a 12 item list to code and score a clinical consultation. It provides a reliable method for detecting differences between the extent of patient involvement with good inter-rater reliability and inter-rater agreement [10, 11]. Raters will be hired graduate students who will be trained in this method, with each rater coding and scoring the first 10 transcripts followed by comparison of the results using the intraclass correlation coefficient (ICC) and its 95% CI before switching to a single rater per transcript method. These scores will be compared between the intervention and control groups for differences in patient involvement using a two-sample t-test and linear regression to adjust for the covariates described in c). We will also compare patient involvement with concordance within groups using t-tests (or regression to adjust for covariates). Finally, we will test whether the relationship between involvement and concordance differs across groups using linear regression and testing for significance of a group*concordance interaction.

g) *Completion or intention to complete therapies.* Group differences in completion or intention to complete recommended therapies will be assessed at 6 months after the clinic visit through chart review of all participants' charts. Intent will be defined as initiation or scheduled initiation of a recommended treatment. The variables of decision made (i.e. type of surgery or sequence of therapy) and completion or intention to complete recommended therapies will be compared between groups using a chi-squared or Fisher's exact test. We will also use a logistic regression framework to test whether the relationship between concordance with completion differs by group. We will consider adjusting for a few covariates described in c), keeping in mind a minimum of 5-10 events per predictor in our models. [12]

Table 2.

Measure Name	Assesses	Prior to Clinic Visit	Immediately After Clinic Visit	2 to 6 Weeks After Clinic Visit	6 Months After Clinic Visit
Patient Preference Scale	Patient's preferred role in decision making process	X			

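### OPTION raters are not masked to group, and the scripted opening of intervention visits probably reveals it, so the between-group OPTION comparison is open to rater bias

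*Combined protocol and SAP*

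**What the plan says.** - **What is rated.** Under Methodology, "all clinic encounters will be digitally recorded, transcribed, and analyzed using the OPTION scale for patient involvement".
- **How transcripts are protected.** Methodology continues: "The transcriptions will be de-identified and coded by independent raters (paid graduate students"). Data Management repeats this: "The digital recordings will be transcribed and de-identified for coding and analysis". Neither place mentions masking to group or study phase.
- **Where the intervention falls.** The Intervention section states "The intervention will take place in the second half of the study", and then "The provider will then have a brief conversation at the beginning of the clinic visit where they state" a set sentence beginning "I see that you prefer to have treatment decisions made", completed with one of three roles. The remainder of the visit is to follow usual practice.
- **What OPTION is for.** Statistical Analysis f): "This scale was developed to measure the extent to which providers involve patients in decisions". It has 12 items, which are not listed. Two trained raters both score the first 10 transcripts, an ICC is calculated, and rating then moves to one rater per transcript.
- **How it is used.** Also in f): "These scores will be compared between the intervention and control groups for differences in patient involvement", by t-test and adjusted linear regression. OPTION is then related to concordance within groups and through a group-by-concordance interaction.
- **Its rank.** The Outcomes section does not list OPTION as primary or secondary. Sample Size Justification gives no figure for it.

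**The concern.** OPTION is the plan's only third-party measure of involvement (Table 2), so it is the one measure of the encounter that could be scored without knowledge of group. As written, it is not. De-identification removes who the patient is. It does not remove a sentence that is planned for one group only and sits at the start of the text.

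Two consequences are possible. A rater who infers the group may score the whole visit more generously, or more severely, than the same behaviour would earn in a control transcript. Separately, the sentence may attract credit as involvement in its own right. In either case a group difference in OPTION could not be read cleanly as a change in how the surgeon involved the patient during the rest of the visit. The Statistical Analysis section intends the results as preliminary data for a larger grant, so an artefact could be carried into the next design.

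**Working it through.** **1. Can the rater see the group?** Set the sections side by side.
- Methodology: the whole encounter is recorded, transcribed and scored.
- Intervention: the sentence is spoken at the start of the visit, in the second half of the study only.
- Methodology, Data Management and f): the stated safeguards are de-identification, independence of raters and training.

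The sentence is therefore in the rated text when delivered as planned, and no stated step takes it out. The documents do not say whether raters are told the design or the phase. Even if they are not, the sentence separates the two sets of transcripts.

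**2. Is there a second rater to offset expectation?** With 100 patients all recorded, 100 − 10 = 90 transcripts have a single rater. Rating order is not stated. If it follows enrolment, all 10 double-rated transcripts come from the first 50 patients, who are all controls, and the ICC would cover no transcript containing the sentence.

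**3. Which OPTION analyses are exposed?** Suppose the artefact adds a constant to every intervention score. It then goes straight into the t-test and into the group term of the adjusted regression; none of the listed covariates measures the rater's knowledge of group, so adjustment does not remove it. A constant cancels from the within-group comparisons with concordance and from the interaction. It would reach those only if it varied with the role named.

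**4. How large could it be?** The plan has no OPTION power, SD or expected difference to reproduce. Its only power figure, 80% for concordance at 50% versus 78% with 50 per group, recomputes to 78.9% by exact enumeration of the two-sided Fisher test and has no bearing here. The following are illustrations on assumed inputs.

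*Credit for the sentence, if any.* Assume 12 equally weighted items and credit on one item. The shift as a share of the total range is credit ÷ 12:
- quarter credit: 0.25/12 = 2.1%
- half credit: 0.5/12 = 4.2%
- full credit: 1/12 = 8.3%

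No credit gives 0. Without an SD, none of these converts to an effect size.

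*False-positive rate.* Assume no true change in provider behaviour and an artefactual shift of d SD in the intervention mean. With n = 50 per group, the two-sided 5% t-test has 50 + 50 − 2 = 98 degrees of freedom and noncentrality d × √(n/2) = 5d. The chance of a significant result is:

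| d (assumed) | Chance of p < 0.05 |
|---|---|
| 0 | 5% |
| 0.1 | 7.9% |
| 0.2 | 16.8% |
| 0.3 | 31.8% |
| 0.4 | 50.8% |
| 0.5 | 69.7% |

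Nothing in the documents ties one sentence, or unmasked rating, to any row.

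**The case against.** The case against has several parts, and most of it stands as a limit on the point.

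- **OPTION ranks low.** It is neither a primary nor a secondary outcome and carries no power claim. This stands.
- **A reader might infer that the trial's only independent check on concordance is compromised.** The documents do not give OPTION that role. Concordance is exact agreement between preferred and achieved role. A patient who prefers to leave all decisions to the doctor, and does so, is concordant with little involvement. OPTION neither confirms nor refutes concordance.
- **A reader might infer that the sentence necessarily raises the score.** The items are not shown, the preference was collected by the research assistant beforehand, and one version of the sentence says the provider will decide. Credit is possible, not demonstrated.
- **Raters are not shown to know the group.** Delivery may be incomplete, and control visits may touch on role preference. Probable inference is as far as the text goes.
- **The conversation is the intervention, so scoring it may be intended.** This is a fair point about the estimand. It does not answer the masking gap, and it can be met by reporting the score both without and with the exchange.

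None of this supplies a safeguard against unmasked rating. The plan already accepts the principle elsewhere: Recruitment keeps providers from administering patient assessments because they deliver the intervention.

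**Conclusion.** The point holds in a limited form. Followed as written, the plan has a between-group outcome scored mostly by one rater, from text that probably discloses the group. That rests directly on the Methodology, Intervention, Data Management and f) text and needs no assumption about OPTION items.

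The size of any bias is unknown. The shifts of 2.1% to 8.3% of range assume equal weights and partial to full credit on one item. The false-positive rates of 7.9% to 69.7% assume shifts of 0.1 to 0.5 SD. They show sensitivity and are not estimates, and the direction of any bias is not established either.

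It would be wrong to read this as a threat to the primary results. Role concordance and satisfaction are reported by patients and are not affected by how transcripts are rated. The change is worth making because it is cheap, fits a step already planned, and must be made before rating starts.

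**What to change.** 1. At de-identification, have the transcriber replace the scripted exchange with a neutral marker, and place the same marker at the start of every transcript in both groups.
2. Withhold study phase and visit date from raters.
3. Supply transcripts in random order, so that the 10 double-rated ones come from both groups.
4. Have the transcriber log whether the sentence was spoken. This gives a delivery rate in the intervention half and a contamination check in the control half.
5. State in f) that the main OPTION comparison uses the masked score for the remainder of the encounter.
6. Once the masked scores are locked, rate the removed exchange and report OPTION with it included as a sensitivity analysis.

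**Cost.** A few minutes per transcript, a short addition to f), and the later rating of the removed exchanges; no extra patients or visits. Random order means that rating waits until intervention visits have been recorded. Masking will be imperfect if the preferred role comes up again later in the visit, and the main score leaves out any real involvement in the opening exchange, which is why the sensitivity analysis is needed.

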2. Investigate the impact of role concordance in the treatment decision making process on short term and long term quality of life and decision outcomes. **We hypothesize that:**
 - a. Patients who achieve role concordance will be more satisfied with the decision process.
 - b. Patients who achieve role concordance will have better QOL and less decision regret at early (2 to 6 weeks) and later (6 months) timepoints after the clinic visit.
 - c. Patients who achieve concordance will be more likely to complete or plan to complete recommended treatments.

Study Subjects: The study population will be newly diagnosed female breast cancer patients scheduled to see one of four breast surgeons at the Huntsman Cancer Hospital Breast Surgery Clinic at the University of Utah. We will exclude patients who have had breast cancer previously, cannot read or write, or have a primary language other than English.

Recruitment: All newly diagnosed patients scheduled in our clinic will be given a recruitment letter as part of their new patient materials (sent the day they scheduled their appointment). They will then be called the day before their visit to gauge interest in participation. If they express interest, they will be sent a consent form electronically so that they can familiarize themselves with the study. They will be asked to arrive at least 30 minutes early for their scheduled appointment (most patients do this anyway) and will be met by a research assistant who will explain the study again and obtain written consent. This same assistant will administer the study scales before and after the clinic visit. Providers will not consent patients nor administer any patient assessments for the study because they will also be delivering the intervention. We expect to enroll a total of 100 patients with 50 in the first year and 50 in the second. We see over 400 new breast cancer patients per year and therefore need approximately 12% of these patients per year to participate in order to reach our recruitment goals. Prior studies using similar methods have had excellent enrollment rates with 98% of eligible patients interested in enrollment.

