Decision scale which combines several elements of decisional satisfaction and is designed to measure satisfaction with the decision regardless of prognosis or outcome [5, 8]. It also correlates with decision confidence. It uses a Likert-type ranking of 6 items related to the decision. The modified version will measure the satisfaction with the process of decision making rather than the decision itself. Group satisfaction differences will be assessed using a two-sample two-tailed t-test. We will also use linear regression to consider adjusting for the potential confounders described above (a-b) along with the following treatment related variables: type of surgery received and the sequencing of treatment (chemo first vs. surgery first), surgical complications, recommendation for chemotherapy, and recommendation for radiation treatment in these analyses. We will also compare satisfaction with concordance within groups using t-tests (or regression to adjust for covariates). Finally, we will test whether the relationship between satisfaction and concordance differs across groups using linear regression and testing for significance of a group*concordance interaction.

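### Type of surgery is compared between groups in all women, including those who could not have breast conservation, and the control for ineligibility named under Outcomes has no method or data source

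*Combined protocol and SAP*

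**What the plan says.** The last sentence under Outcomes plans to relate two exposures, the patient's preferred role and her concordance, to "type of surgery received or planned, controlling for ineligibility for breast conservation". Study group is not an exposure there.

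Study Subjects does not limit entry by surgical options: "We will exclude patients who have had breast cancer previously, cannot read or write, or have a primary language other than English". Women who cannot have breast conservation are therefore enrolled.

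In the Statistical Analysis, type of surgery is an outcome only in item g). Data come "through chart review of all participants' charts". The sentence that opens "The variables of decision made (i.e. type of surgery or sequence of therapy" goes on to say that these variables, with completion of therapy, "will be compared between groups using a chi-squared or Fisher's exact test". The groups are the first 50 and the next 50 patients.

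The one regression in g) is there "to test whether the relationship between concordance with completion differs by group", so its outcome is completion. Its optional covariates are those of item c): age, education and stage carried over from a-b), plus "type of surgery received and the sequencing of treatment (chemo first vs. surgery first), surgical complications, recommendation for chemotherapy, and recommendation for radiation treatment". Ineligibility for breast conservation is in neither list.

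**The concern.** A woman who cannot have breast conservation does not choose between it and mastectomy, so her operation says nothing about how the decision was shared. The protocol recognises this under Outcomes but does not carry it into the analysis. Two gaps follow.

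1. The analysis promised under Outcomes has a stated control but no model, no test and no named source for the controlling variable.
2. The surgery-type test that is specified, in g), pools women with and without a choice. Ineligible women push both groups towards mastectomy, which narrows a real difference. Because the groups are consecutive and not randomised, a change in case mix between periods would also appear as an effect of the intervention on surgery.

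The study is meant to supply preliminary data for a larger grant application, so a misleading surgery result could be carried forward.

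**Working it through.** **Inputs from the documents.** 50 patients per group, enrolled in sequence (Statistical Analysis); Fisher's exact test (item g); two-sided 0.05 level, borrowed from Sample Size Justification.

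**Assumed, because the documents give no figures.** Surgery is mastectomy or breast conservation; ineligible women have mastectomy 100% of the time; the ineligible share q runs from 0% to 40%; the mastectomy rate p in eligible women is 40% in both groups (no effect) or 30% versus 58% (true effect).

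**Check of the method.** No power is stated for type of surgery. The only power figure is 80% for a 28-point rise in concordance with 50 per group. Taking 50% versus 78% and enumerating every pair of outcomes from Binomial(50, 0.50) and Binomial(50, 0.78) gives exact Fisher power of 78.9%, close to the stated 80%. The same enumeration is used below.

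**Formula.** Mastectomy rate in a whole group: m = q + (1 − q)p.
- Same q in both groups: difference = (1 − q)(p2 − p1).
- Same p in both groups: difference = (q2 − q1)(1 − p).

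**Dilution: true rates 30% versus 58% in eligible women, q equal in both groups**

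| q | All women, m1 vs m2 | Difference | Fisher power, all women | Fisher power, eligible only (n per group) |
|---|---|---|---|---|
| 0% | 30.0% vs 58.0% | 28.0 points | 77% | 77% (50) |
| 10% | 37.0% vs 62.2% | 25.2 points | 67% | 69% (45) |
| 20% | 44.0% vs 66.4% | 22.4 points | 56% | 66% (40) |
| 40% | 58.0% vs 74.8% | 16.8 points | 35% | 50% (30) |

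For example, at 20%: 0.20 + 0.80 × 0.30 = 0.440 and 0.20 + 0.80 × 0.58 = 0.664. Eligible-only power uses the expected number, 50(1 − q). Restriction loses patients but gains power.

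**False difference: no effect, 40% mastectomy in eligible women of both groups**
- q = 20% in both: 0 points; Fisher's test rejects 3.5% of the time.
- 15% vs 25%: 0.10 × 0.60 = 6 points; rejects 7%.
- 10% vs 30%: 0.46 vs 0.58, or 0.20 × 0.60 = 12 points; rejects 18%.
- 10% vs 40%: 0.30 × 0.60 = 18 points; rejects 38%.

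**Both together.** With true rates of 30% vs 58% and ineligible shares of 30% vs 10%: 0.30 + 0.70 × 0.30 = 0.510 and 0.10 + 0.90 × 0.58 = 0.622. The 28-point difference appears as 11 points, with 16% power.

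**Chance imbalance.** If the true ineligible share is the same in both periods, a gap of at least 10 points still arises with probability 13%, 26% or 33% at a true share of 10%, 20% or 30%. Such a gap moves the individual result but is already counted in the test's error rate, hence the 3.5% above. A real shift in case mix between periods is not.

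**The case against.** The strongest reply is that Outcomes and g) describe different analyses. This stands. A reader might infer that g) contradicts Outcomes; it does not. In a combined protocol and SAP, a control stated once under Outcomes is not cancelled because g) does not repeat it.

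A reader might also infer that g), as written, would report more mastectomies in discordant women. The documents do not support that. The surgery-type test in g) is by study group, and its concordance model has completion as the outcome. The only text that names surgery by concordance is under Outcomes, where the control is stated. A size for that bias would apply only if the stated control were ignored, and it depends on an unsupported assumption about concordance. With 35% mastectomy in eligible women and 15%, 25% or 35% ineligible, concordance of 60% in eligible and 30% in ineligible women gives false gaps of about 10, 15 and 18 points. Concordance of 60% and 50% gives about 3, 5 and 6, and equal concordance gives none.

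Two further inferences fail. No model in g) adjusts type of surgery for itself. The absence of eligibility from Table 2 proves little, since that table lists scales only and also omits age and stage.

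The Overview expects similar populations and plans to examine pre/post differences. That helps only if eligibility is recorded, and it does nothing about dilution, which occurs with perfect balance. Stage may track eligibility in part, but the plan offers it only as an optional covariate in regression models, not in the chi-squared or Fisher comparison.

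Finally, type of surgery is neither a primary nor a listed secondary outcome. This stands and limits the weight of the point.

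**Conclusion.** The point holds in two parts. First, the analysis of surgery type by preferred role and concordance has a promised control but no method and no named source for ineligibility. Second, the comparison of surgery type between groups in g) is unadjusted and includes women who had no option of breast conservation.

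If ineligible women nearly always have mastectomy, dilution follows for any share above zero: 28 points become 22 at 20% ineligible and 17 at 40%. A false difference needs the share to differ between periods; 10% versus 30% gives 12 points. These sizes rest wholly on assumed rates. If few enrolled women are ineligible, the effect is small. The primary concordance result and the listed secondary outcomes are not touched. This is a cheap improvement to an exploratory analysis.

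**What to change.** 1. Make eligibility for breast conservation a defined item in the planned 6-month chart review. Base it on reasons documented at the time of the surgical decision, and abstract it without reference to study group. A judgement asked of the surgeon after the visit is less suitable, because in the second half that surgeon knows the preferred role and has delivered the intervention.
2. In g), analyse type of surgery by study group, and by preferred role and concordance as Outcomes promises, among eligible women or stratified by eligibility (for example Mantel-Haenszel). If every ineligible woman has a mastectomy, her stratum adds nothing to the Mantel-Haenszel odds ratio or test, so the two routes then agree.
3. Report ineligible women descriptively, with their number in each group.
4. In these models, do not adjust for variables that are, or follow from, the operation: type of surgery, surgical complications and, where it depends on the operation, the radiation recommendation.

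Cost: one extra abstracted item, some added wording in g), and a smaller number in an exploratory analysis (about 40 rather than 50 per group if 20% are ineligible). Eligibility is still recorded after the visit, so the definition should leave little room for judgement.
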